### 7.2.1 Inclusion Criteria

1. A male or female patient (of any age) with genetically confirmed diagnosis of ALGS. A patient may be randomized based on genetic testing results in the medical record. If genetic testing results are not available, testing will be performed at Screening Visit 1, and the patient may not be randomized until the genetic diagnosis is confirmed
2. Patient must have a history of significant pruritus and a caregiver reported observed scratching or a patient-reported pruritus score at an average of  $\geq 2$  (on 0 to 4 scale), as measured by the Albireo ObsRO instrument (for patients  $< 18$  years of age) or the PRO instrument (for patients  $\geq 18$  years of age) in the 14 days prior to randomization. For each AM and PM weekly assessment a minimum of 4 out of 7 expected scores must be recorded. The mean of the weekly AM and the mean of the weekly PM scores will be averaged to determine the pruritus score as measured by ObsRO or PRO, if the patient is  $\geq 18$  years of age
3. Patient must have an elevated baseline serum bile acid level. Each of the serum bile acid levels obtained at Screening Visit 1 and Screening Visit 2 must be greater than the upper limit of normal ( $> \text{ULN}$ )
4. Patient and/or legal guardian must sign informed consent (and assent) as appropriate. Patients who turn 18 years of age (or legal age per country) during the study will be required to re-consent in order to remain in the study
5. Caregivers must be willing and able to use an eDiary device as required by the study and patients  $\geq 8$  years of age must be willing to use an eDiary if able to do so
6. Sexually active males and females must agree to use a reliable contraceptive method with  $\leq 1\%$  failure rate (such as hormonal contraception, intrauterine device, or complete abstinence) throughout the duration of the study and 90 days thereafter (from signed informed consent through 90 days after last dose of study drug). See [Appendix 6](#) for further details

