Age is the stratification factor for the study. Since the purpose of stratification in the randomization is to balance the treatments in each stratum and following the intend-to-treat principle, for any analysis based on the FAS where strata is used for covariate adjustment of the modeling (with the exception of subgroup analyses), the strata of age that is recorded in the randomization system (IWRS) will be used. For all other analyses based on the FAS and all subgroup analyses, the actual age will be used to categorize the age groups.

Selected patient data, including derived data, will be presented in individual patient data listings. All listings will be sorted by treatment group, patient number, date/time and visit. Each patient’s sex and age at randomization will be stated on each listing. Data listings will be based on all randomized patients.

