Patients (\geq 5 years) and caregivers will be asked to complete a quality-of-life questionnaire (PedsQL) at Randomization Day 1, Week 12, and Week 24. Details of the questions included on the questionnaire are provided in Protocol Appendix 4. Comparisons of the change from baseline at Week 12 and Week 24 in the PedsQL total score (calculated as average score of all answered items) and domain scores between the treatment groups will be conducted using ANCOVA. The model will include terms for baseline, age category based on the age groups defined for the PedsQL (5 to $<$ 8, 8 to $<$ 13, 13 to $<$ 18) and treatment. The analysis will be conducted based on the total scores reported by child (\geq 5 years of age) and by parent (including patients for all age) separately. If the sample size based on child reported data (\geq 5 years of age) is less than 10, then ANCOVA will not be conducted. The PedsQL total score and domain scores of the family impact module will be analyzed similarly.

A Pearson correlation coefficient will be provided to evaluate the relationship between the primary endpoint (change from baseline in scratching score to Month 6 (Weeks 21 to 24)) and the key secondary endpoint (change in serum bile acid levels from baseline to the average of Week 20 and Week 24).

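### The PedsQL ANCOVA's age term starts at 5 years, but the parent-report analysis is meant to cover all ages, so children under 5 have no covariate value

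*SAP*

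**What the plan says.** SAP 4.6.4.1 plans an ANCOVA at two visits: "Comparisons of the change from baseline at Week 12 and Week 24 in the PedsQL total score", together with the domain scores. Besides baseline, the model contains "age category based on the age groups defined for the PedsQL (5 to $<$ 8, 8 to $<$ 13, 13 to $<$ 18) and treatment". No other age term appears anywhere in the PedsQL text.

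The paragraph then names two analyses under this one specification. The first uses scores reported by children aged 5 or over. The second uses scores reported "by parent (including patients for all age) separately". The only fallback concerns the child report: if its sample size "is less than 10, then ANCOVA will not be conducted". A further instrument follows the same approach: "The PedsQL total score and domain scores of the family impact module will be analyzed similarly".

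Protocol 7.2.1 sets no lower age limit: "A male or female patient (of any age) with genetically confirmed diagnosis of ALGS". Protocol 9.2.3 asks patients and caregivers for the PedsQL without stating a minimum age.

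**The concern.** The three age levels fit the child report exactly, because that report begins at 5 years. They do not fit the parent report. A four-year-old can have a parent score at baseline and at Week 24, a treatment assignment, and no value for one of the model's classification terms. The SAP gives no level, alternative covariate or handling rule for that child.

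Standard ANCOVA procedures delete a record with a missing classification variable, usually without more than a line in the output. An analysis described as covering all ages would then describe children aged 5 and over. Under the SAP, children under 5 give no PedsQL self-report, so the parent report is their only PedsQL information on the child. In a trial of about 45 patients, losing usable records is worth avoiding when one sentence prevents it.

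**Working it through.** **1. Are children under 5 expected?** Yes, from several places besides the inclusion criterion:

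- SAP 4.5.3 and 4.6.3 define a subgroup of 0 to <2 years.
- SAP 4.6.4 specifies a separate growth method for patients under 2 years.
- Protocol Table 2 starts dosing weights at 4.0 kg, and Protocol 8.2 covers infants not yet on solid food.
- Protocol 9.2.2 allows a fasting exception for infants under 12 months.

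**2. Do the levels cover the stated population?**

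| Analysis | Stated ages | Ages covered by the age term | Gap |
|---|---|---|---|
| Child report | 5 to <18 | 5 to <18 | none |
| Parent report | all, so 0 to <18 | 5 to <18 | 0 to <5 |
| Family impact module | not stated | not stated; handled in a similar way | 0 to <5 if the same term is used |

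**3. What does fitting the model as written do?** An ANCOVA with baseline, the three-level age category and treatment was fitted to 45 made-up records, 30 active and 15 placebo, with ages drawn uniformly from 0 to 18. Eleven records were under 5. The model used 34 of 45. With a fourth level for 0 to <5 it used all 45. This shows the mechanism only; the ages are invented.

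**4. How large is the loss?** The plan gives no sample size or power for PedsQL, so there is no PedsQL figure to reproduce. Its general sample-size inputs (SAP 2.1) are 45 randomised 2:1, 20% drop-out and 36 completers. The stated primary-endpoint power of 0.909 reproduces: a one-sided t test at 0.025 with 24 against 12, difference 1.2 and SD 1.0 gives 0.9094. I take only the numbers and the allocation from it.

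With N children split 2:1 and residual SD σ, the standard error of the treatment difference is σ·√(1/(2N/3) + 1/(N/3)) = σ·√(4.5/N). If a share f is excluded and the split is unchanged, N becomes N(1 − f), so the standard error is multiplied by 1/√(1 − f). The share f is an assumption:

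| Assumed share under 5 | Kept of 45 | Kept of 36 completers | Multiplier 1/√(1 − f) |
|---|---|---|---|
| 20% | 36.0 | 28.8 | 1/√0.8 = 1.12 |
| 30% | 31.5 | 25.2 | 1/√0.7 = 1.20 |
| 50% | 22.5 | 18.0 | 1/√0.5 = 1.41 |

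A wider range of 10% to 60% gives 1.05 to 1.58. The multiplier is the same whether one starts from 45 or 36.

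**The case against.** The SAP never says that children under 5 are left out. Its one explicit statement about the parent-report population is that all ages are in. The levels may be an incomplete list: they match the self-report range with which the paragraph opens, and a younger level may have been intended and not written down. A programmer who noticed could add one. The documents that might settle it cannot be consulted: the sample SAS code in SAP Appendix 6 is redacted, and Protocol Appendix 4 is not in the text available for this review.

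This stands in part. Exclusion is what happens if the model is fitted as written; it is not a stated rule and not certain. The mismatch between the levels and the population remains on either reading, because any repair made in programming would be a choice that the SAP does not specify.

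Two further inferences should be resisted:

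- **That the model breaches SAP 4.1.** That section says "Age is the stratification factor for the study" and asks for the IWRS value where the stratum is used as a covariate. The PedsQL model deliberately uses a different term, an "age category based on the age groups defined for the PedsQL". That is a permitted choice, not a contradiction.
- **That the family impact module certainly has the same gap.** The SAP says only that it is handled in a similar way and does not name its age term.

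**Conclusion.** The point holds as a mismatch within SAP 4.6.4.1: the age levels do not cover the population stated for the parent report. If the model is fitted as written, children under 5 drop out of the parent-report analysis, and out of the family impact analysis if it uses the same term.

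A reader might infer that the treatment estimate would be biased. The documents do not support that. Exclusion would depend on age before treatment, so the comparison among children aged 5 and over would still be randomised. The harm is lost precision and a narrower population than the plan states.

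The size is illustrative: a standard error about 12%, 20% or 41% larger if 20%, 30% or 50% of children are under 5. It rests on an assumed age mix, equal residual variance across ages and the same 2:1 split among those kept. It ignores the small effect of changes in degrees of freedom.

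The child-report analysis is not affected. PedsQL is outside the hierarchical testing in SAP 4.7, so the primary and key secondary conclusions are unaffected.

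**What to change.** In SAP 4.6.4.1, give the parent-report and family impact ANCOVA an age term that is defined for every child, and state which term it is. The smallest change is a fourth level below 5 years, which keeps the plan's adjustment for instrument age group. The IWRS age stratum (<10, 10 to <18) would also do: it covers every child and is already used in the primary and key secondary models. Keep the three existing levels for the child report. If a restriction to 5 years and over was in fact intended, the SAP should say so and drop the reference to all ages.

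The cost is one sentence and no new data. A fourth level uses one more model parameter. The change should be made before database lock and unblinding; the number of children under 5 can be counted from blinded demographic data.

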4.6.4.2 Categorical Endpoints

A clinically meaningful decrease in scratching score will be defined in the psychometric analysis report based on psychometric analysis results before database lock. Please refer to the

psychometric analysis plan for details. The results of the blinded psychometric analysis across all anchors and timepoints supported a threshold from 1.0 to 1.5 points. The upper bound of 1.5 points reduction will be used for the primary analysis while the lower bound of 1.0-point reduction will be used for the sensitivity analysis. The proportion of patients achieving a clinically meaningful decrease in scratching score (pruritus responders) at Week 24 (or Week 12) will be analyzed using a Cochran-Mantel-Haenszel (CMH) test. Patients with missing data at Week 24 (or Week 12) will be classified as non-responders. CMH stratified by baseline age stratification will be performed to compare the proportion of the responders in pruritus at Week 24 (or Week 12). In the CMH test, data in a stratum will not be used in the calculation of the p-value if a row sum or column sum is 0 in the contingency table. If a row sum or column sum is 0 or a stratum has <4 patients, the CMH test will not be stratified.

The clinician xanthoma scale uses a 5-point scale, in which 0 represents no evidence of xanthomatosis, 1 represents fewer than 20 scattered individual lesions, 2 represents more than 20 lesions that do not interfere with or limit activities, 3 represents large numbers of lesions that by their large numbers or size cause distortion of the face or extremities, and 4 represents xanthomas that interfere with function (such as hand use or ability to walk) because of excess size or number. The change from baseline to Week 12, Week 24 and last assessment during treatment in xanthomatosis will be summarized by a shift table. Shift tables for the number of patients with changes from baseline to the best and to the worst post-baseline value will be provided.

Patients (≥ 8 years of age), caregivers, and clinicians will complete GIC (PGIC, CaGIC, and CGIC) and the GIS measures (PGIS, CaGIS, CGIS) (Protocol Appendix 3) at randomization (Study Day 1; PGIS only), Week 4, 12, and 24. The GIC items that assess change in itch (patient version), scratching (caregiver and clinician version), and sleep (all version) will be analyzed using the proportional odds model with treatment and baseline GIS score as the covariates and will consider 3 categories (better, no change, worse). The better category will include answers of “Very Much Better”, “Much Better”, and “A Little Better”; no change will include answers of “No Change”; worse will include answers of “A Little Worse”, “Much Worse”, and “Very Much Worse”. GIC and GIS data at baseline (GIS only), Weeks 4, 12, and 24 will be summarized using frequency tables and bar chart figures.

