1.2 Objective and Endpoints

The primary, key secondary, and secondary efficacy objectives, and safety objectives and endpoints are listed in [Table 2](#).

Table 2 - Objectives and endpoints

Objectives	Endpoints

Primary Efficacy
 
 To demonstrate the efficacy of repeated daily doses of 120 µg/kg/day odevixibat in relieving pruritus in patients with ALGS 	
 Change from baseline in scratching score to Month 6 (Weeks 21 to 24) as measured by the Albireo Observer reported outcome (ObsRO) caregiver instrument

Key Secondary Efficacy
 
 To assess the impact of odevixibat on serum bile acid levels in patients with ALGS 	
 Change in serum bile acid levels from baseline to the average of Week 20 and Week 24

Secondary Efficacy
	
 Change from baseline in pruritus score to Month 6 (Weeks 21 to 24) as measured by the Albireo Patient reported outcome (PRO) instrument Percentage of patients achieving a clinically meaningful decrease in pruritus (pruritus responders) as measured by the Albireo ObsRO/PRO instruments Change from baseline through Week 24 in patient reported and observer reported itching and scratching severity scores, respectively, for the morning assessment and for the evening assessment. These endpoints will be assessed combining age groups, and by age group, 0 to <8, 8 to <12, and 12 to <18 Change from baseline to Week 24 in sleep parameters as measured with the Albireo ObsRO/PRO instruments (e.g., tiredness and number of awakenings)

Objectives	Endpoints

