4.5.2 Estimand

The primary objective of this study is to assess the efficacy of repeated daily doses of 120 µg/kg/day odeixibat in relieving pruritus in patients with ALGS. The estimand includes all data collected through the end of the study following an ICE due to premature discontinuation of study treatment prior to Week 24 (i.e., treatment policy strategy), while excluding data following ICEs of biliary diversion surgery or liver transplant (i.e., hypothetical strategy).

On the one hand, premature treatment discontinuation could occur due to an AE, tolerability issue, lack of efficacy, or other reasons. As stated in the guidance for industry E9(R1) Statistical Principles for Clinical Trials: Addendum: Estimands and Sensitivity Analysis in Clinical Trials, the clinical and regulatory interest of hypothetical scenarios assuming the patient could tolerate treatment or did not have an AE is limited and would usually depend on a clear understanding of why and how the intercurrent event or its consequences would be expected to be different in clinical practice than in the clinical trial. Therefore, the estimand will utilize the treatment policy strategy for premature treatment discontinuation ICEs and include all data collected after this type of ICEs. This reflects the patients' outcomes in practice if they are unable to continue receiving the investigational drug. Of note, protocol section 7.1.4 specifies that for patients who prematurely discontinue study drug treatment during the treatment period, all efforts will be made to have patients continue to complete all scheduled study visits for assessments following completion of the EOT visit.

On the other hand, only a small number of patients, if any, are expected to have biliary diversion surgery or liver transplant during the placebo-controlled portion of the trial. As biliary diversion surgery may be viewed as a "rescue" treatment for pruritus, it may be reasonable for the primary analysis of pruritus outcomes to utilize a hypothetical strategy (which assumes that the biliary diversion surgery did not occur) for this ICE. A similar strategy may be reasonable for liver

transplantation, although transplantation may be indicated for reasons other than pruritus. The proposed primary analysis method will model outcomes following biliary diversion surgery or liver transplantation informed by the patients' outcomes prior to the surgery/transplant and by the trajectories of other patients in the trial.

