4.6.4 Other Secondary Endpoints

For all secondary endpoints, all data collected through the end of the study following an ICE due to premature discontinuation of study treatment prior to Week 24 (i.e., treatment policy strategy), will be included while excluding data following ICEs of biliary diversion surgery or liver transplant (i.e., hypothetical strategy).

The change in secondary endpoints such as serum bile acids, ALT, AST, gamma-glutamyl transferase, direct bilirubin, total bilirubin, total cholesterol, PRO and ObsRO sleep parameters will be summarized by visit using descriptive statistics.

In addition to evaluate vital signs (height and weight) in the safety analysis, growth data (height/length for age, weight for age, and BMI for age) will be considered as an exploratory efficacy endpoint. Growth data will be calculated using the software or methods from the Centers for Disease Control and Prevention (CDC) website [12] for patients with age ≥ 2 years old and from the World Health Organization (WHO) website [13] for patients with age < 2 years old.

Change from baseline in growth (i.e., height [cm], weight [kg], BMI [kg/m²] and corresponding linear growth compared to a standard growth curve [Z-score, SD from P50 standard growth curve], calculated by using the software or methods from the CDC website for patients with age \geq 2 years old and from the WHO website for patients with age $<$ 2 years old) will be summarized by visit using descriptive statistics.

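### The SAP states a hypothetical strategy for surgery for all secondary endpoints, but its responder rule scores the resulting missing data as failure, and no sensitivity analysis covers missing responder data

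*SAP*

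**What the plan says.** The responder percentage is a listed secondary endpoint (SAP 1.2, Table 2): "Percentage of patients achieving a clinically meaningful decrease in pruritus (pruritus responders) as measured by the Albireo ObsRO/PRO instruments".

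SAP 4.6.4 sets the intercurrent-event strategy for this whole class. Its scope is explicit: "For all secondary endpoints, all data collected through the end of the study following an ICE due to premature discontinuation" of study treatment are to be used (treatment policy). For surgery it specifies "excluding data following ICEs of biliary diversion surgery or liver transplant (i.e., hypothetical strategy"). SAP 4.5.2 explains the label for the primary endpoint as a strategy "which assumes that the biliary diversion surgery did not occur", with later outcomes modelled from the patient's own earlier scores and from other patients' trajectories.

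SAP 4.6.4.2 defines the responder analysis, a Cochran-Mantel-Haenszel test stratified by age. On missing data it says: "Patients with missing data at Week 24 (or Week 12) will be classified as non-responders". It makes no exception for scores removed because of surgery. On thresholds it says: "The upper bound of 1.5 points reduction will be used for the primary analysis while the lower bound of 1.0-point reduction will be used for" sensitivity. No other sensitivity analysis is given for this endpoint.

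Protocol 11.2.2.2 says that sensitivity analyses, multiple imputation among them, will examine how robust the efficacy results are and will be set out in the SAP. The SAP specifies control-based imputation and a tipping-point analysis for the primary endpoint (4.5.2.2.1, 4.5.2.2.2) and for serum bile acid (4.6.2.2.1, 4.6.2.2.2).

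**The concern.** A hypothetical strategy and non-responder classification answer different questions about a patient who has surgery. The first asks what the score would have been without surgery. The second treats the surgery itself as an unfavourable outcome. The SAP declares the first and, for responders, carries out the second. A study report that copies the stated estimand would then describe the responder percentage wrongly.

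The second part is separate. Non-responder classification makes the observed rate depend on how much data are missing in each arm. Changing the threshold from 1.5 to 1.0 points does not test that dependence, so a reader of the responder result has no planned way to judge it.

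**Working it through.** **The texts side by side**

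1. SAP 4.6.4: scores after biliary diversion or transplant are removed, for every secondary endpoint.
2. SAP 4.6.4.2: a patient without data at the assessment is a non-responder. This is the only rule given for an absent responder value.
3. Together: if surgery leaves too little earlier data for a score, the patient is a failure. That is a composite strategy in effect.
4. SAP 4.5.2: the declared strategy assumes no surgery and models the outcome. Steps 3 and 4 do not agree.

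The conflict arises only when no evaluable score remains. If response uses the monthly score, three of four weekly scores suffice (SAP Appendix 2, Table 9), so surgery late in Weeks 21 to 24 could leave a valid score. SAP 4.6.4.2 does not say whether the weekly or the monthly score is meant.

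**Size through surgery**

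Inputs: 45 randomised 2:1 (SAP 2.1), that is 45 × 2/3 = 30 on odevixibat and 45 × 1/3 = 15 on placebo. One patient changes an arm's rate by at most:

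- odevixibat: 1/30 = 3.3 points
- placebo: 1/15 = 6.7 points

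**Size through other missing data**

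The plan gives no responder rate or responder power to reproduce. Its sizing figures do reproduce: 36/(1 − 0.20) = 45, and the exact t-test power for 24 against 12 completers, difference 1.2, SD 1.0, one-sided 0.025, is 0.9094 against the stated 0.909. Nothing here rests on them.

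If missingness is unrelated to outcome, observed rate = true rate × (1 − missing share). Illustration with the plan's SD of 1.0 and difference of 1.2, the 1.5-point threshold, normally distributed changes, and an assumed mean placebo reduction of 0.3:

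- true odevixibat rate: Φ(0.3 + 1.2 − 1.5) = Φ(0) = 50.0%
- true placebo rate: Φ(0.3 − 1.5) = Φ(−1.2) = 11.5%
- true difference: 38.5 points

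| Missing, odevixibat / placebo | Observed rates | Difference |
|---|---|---|
| 0% / 0% | 50.0% / 11.5% | 38.5 |
| 20% / 20% | 40.0% / 9.2% | 30.8 |
| 10% / 20% | 45.0% / 9.2% | 35.8 |
| 20% / 10% | 40.0% / 10.4% | 29.6 |

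With an assumed placebo reduction anywhere from 0 to 0.5, the true difference is 31.5 to 42.1 points. With 20% missing in both arms it becomes 25.2 to 33.6 points. The one-fifth shrinkage does not depend on the assumed rates, because both rates are multiplied by 0.8.

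**The case against.** Much of the case on the other side stands.

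- **Surgery will be rare.** SAP 4.5.2 expects few such patients, if any, and exclusion criterion 10 bars a transplant planned within 6 months. The mismatch may affect nobody.
- **The SAP does not say that excluded scores count as missing.** That is an inference, though no other rule is offered.
- **Non-responder classification is a recognised convention.** Scoring ordinary missing data as failure does not contradict SAP 4.6.4; the contradiction is confined to surgery and transplant.
- **Missingness will be visible.** SAP 4.2 tabulates discontinuation and withdrawal with reasons and makes a missing Month 6 score an important deviation. SAP section 3 summarises reasons for per-protocol exclusion by treatment group. The underlying scratching score has its own imputation and tipping-point analyses. What is absent is a check on the dichotomised result.
- **The endpoint is supportive,** without alpha control (SAP 4.7).

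Two stronger readings are tempting and should be resisted. A reader might take the 20% drop-out allowance in SAP 2.1 as the expected missing-data rate. It is a sizing allowance; scores after treatment discontinuation are kept, and Protocol 7.1.4 asks that visits continue.

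A reader might also infer that the rule favours odevixibat. With 10% missing on odevixibat and 30% on placebo, the rate ratio in the illustration does rise, from 50.0/11.5 = 4.3 to 45.0/8.05 = 5.6. The difference nevertheless falls, from 38.5 to about 37 points, and the SAP plans no ratio. The difference grows only if the placebo rate times its missing share exceeds the same product for odevixibat. The documents do not establish either direction.

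**Conclusion.** The point holds in two limited parts. First, the strategy stated in SAP 4.6.4 and the rule in 4.6.4.2 do not match for patients who have surgery or transplant before the assessment and have no evaluable score. The numerical effect is probably small: at most 3.3 or 6.7 points in an arm's rate per such patient, with few expected. Second, no sensitivity analysis addresses missing responder data, although the protocol foresees such analyses for efficacy results. The size of that effect is unknown beforehand. The one-fifth shrinkage assumes 20% missing in both arms and missingness unrelated to outcome; the responder rates used to illustrate it are also assumed.

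Neither part touches the primary or key secondary test. This is an inexpensive improvement to a supportive endpoint, not a threat to the trial's conclusion.

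**What to change.** 1. In SAP 4.6.4, exempt the responder endpoint from the hypothetical strategy.
2. In SAP 4.6.4.2, state that biliary diversion surgery or liver transplant before the assessment is analysed as non-response (composite strategy). Keep non-responder classification as the main rule for all other missing data.
3. State that response is based on the Month 6 (or Month 3) monthly ObsRO score.
4. Add one supportive analysis. Take the MAR-imputed monthly ObsRO scores from step 1 of the tipping-point analysis (SAP 4.5.2.2.2), subtract baseline, and dichotomise at 1.5 and at 1.0 points. Keep patients with prior surgery or transplant as non-responders.
5. Report an age-stratified Mantel-Haenszel risk difference for both the main and the imputed analysis, so that the two can be compared. Combine the imputed estimates by Rubin's rules.

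The cost is a few sentences and one extra table, with no new data and no change to an alpha-controlled test. SAP 4.6.2.3.1 already makes similar use of the step 1 imputation for serum bile acid. Reuse works only if item 3 is adopted; a weekly score would need its own imputation. PRO responders would also need a separate imputation and can be left out of the supportive analysis.
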